#### 4.1.5.1 Study oversight

The SMC will convene after the last participant in a given cohort has completed the required 28-day DLT Observation Period. The SMC will decide whether to halt dose escalation, further expand the dose level to gain additional safety data, or determine the next dose level to be tested.

Safety conference calls with investigators and key Sponsor personnel will be held regularly.

#### **4.1.5.2 Dose-limiting toxicity determination and maximum tolerated dose definition**

##### **4.1.5.2.1 Definition of DLT**

Dose-limiting toxicity is defined as one of the following toxicities (according to the NCI CTCAE Version 5.0) occurring during the DLT assessment window (Days 1 to 28 of Cycle 1) that is at least possibly related to UCB6114:

- Grade  $\geq 4$  neutropenia (ANC  $< 500/\mu\text{L}$ ) lasting  $\geq 7$  days
  - In the event of CTCAE Grade 4 neutropenia, full blood count must be performed on the seventh day after the onset of the event to determine if a DLT has occurred
- Grade  $\geq 3$  neutropenia complicated by fever ( $\geq 38^\circ \text{C}$ ) or infection
- Grade 3 thrombocytopenia with bleeding or requiring platelet transfusion or Grade 4 thrombocytopenia
- Any Grade  $\geq 3$  non-hematological event with the following exceptions:
  - Grade 3 nausea, vomiting, diarrhea, or fatigue that resolves to Grade  $\leq 2$  within 24 hours of implementing optimal supportive care
  - Grade 3 laboratory abnormality that is asymptomatic and also deemed by the investigator to not be clinically significant

Investigators, in consultation with the medical monitor, can declare a DLT if a participant is experiencing toxicity and treatment cannot be continued without exposing the participant to excessive risk.

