##### **4.1.5.2.2 Determination of maximum-tolerated dose**

For every dose levels, participants will be treated in cohorts of 2 to 4 (target of 3), each dose level will have a minimum of 3 and a maximum of 9 participants.

The target rate of DLTs is 25% (equivalence interval 20% to 30%). The target rate will define the MTD of the combination regimen (UCB6114 given in combination with mFOLFOX6).

The mTPI method relies upon a statistical probability algorithm, calculated using data from all participants treated in prior and current cohorts at the same dose level, to determine whether future cohorts should be dose escalated, have no change in dose, or be dose de-escalated. The dose escalation will stop if any of the following criteria are met:

- The maximum sample size has been reached (27 participants total)
- At least 9 participants have been accumulated on a dose that is predicted to be the MTD
- All doses explored appear to be overly toxic and the MTD cannot be determined
- The escalation would exceed a dose level tested and considered safe by the SMC in monotherapy (Part A)

The mTPI design uses a Bayesian decision framework to inform dose-escalation and de-escalation decisions. These rules are conceptually similar to those used by the 3+3 design. The

dose-escalation decisions can be pre-calculated under the mTPI design and are presented in a 2-way table (Table 4-3).

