**Table 6-9: TFD/TPI dose modifications in case of hematological and non-hematological toxicities**

Adverse reaction	Recommended dose modifications
Febrile neutropenia, CTCAE Grade 4 neutropenia (<0.5x10  /L) or thrombocytopenia (<25x10  /L) that results in more than 1 week's delay in start of next cycle. CTCAE Grade 3 or Grade 4 nonhematologic AEs; except for Grade 3 nausea and/or vomiting controlled by antiemetic therapy or diarrhea responsive to antidiarrheal medicinal products.	Interrupt dosing until toxicity resolves to Grade 1 or baseline. When resuming dosing, decrease the dose level by 5mg/m  /dose from the previous dose level ( Table 6-10 ). Dose reductions are permitted to a minimum dose of 20mg/m  /dose bid. Do not increase dose after it has been reduced.

AE=adverse event; bid=twice daily; CTCAE= Common Terminology Criteria for Adverse Events; TFD/TPI=trifluridine/tipriacil

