**Table 6-14: Dose modification for hematological toxicity**

Prior to Dosing (Day 1 or Day 15)	Toxicity		Dose level for subsequent cycles	
	CTCAE (V5.0) Toxicity Grade	Platelets ( $\times 10^9/L$ )	Oxaliplatin	5-Fluorouracil
If ANC is $\geq 1.2$ within 2 weeks, proceed with treatment at a dose level according to the lowest ANC result of the delayed weeks.	4	<0.5	Reduce 1 dose level	Omit iv bolus and reduce infusion 1 dose level
If ANC remains <1.2 after 2 weeks, discontinue treatment.				
If platelets <75 on Day 1 or Day 15, hold treatment. Perform weekly blood counts.	1	$\geq 75$	Maintain dose level	Maintain dose level
If platelets $\geq 75$ within 2 weeks, proceed with treatment at a dose level according to the lowest platelets result of the delayed weeks.	2	50 to <70	Maintain dose level	Maintain dose level
If platelets remain <75 after 2 weeks, discontinue treatment.	3	10 to <50	Reduce 1 dose level	Maintain dose level
	4	<10	Reduce 2 dose levels	Maintain dose level

ANC=absolute neutrophil count; CTCAE= Common Terminology Criteria for Adverse Events; iv=intravenous(ly)

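### Table 6-14 (Part C) and Table 6-9 (Part B) give different platelet counts for CTCAE Grade 4 thrombocytopenia, and the Part C DLT criterion prints no count to settle it

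*Protocol*

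**What the plan says.** **DLT criterion.** Protocol sections 4.1.4.2.1 (Part B) and 4.1.5.2.1 (Part C) use the same platelet wording: "Grade 3 thrombocytopenia with bleeding or requiring platelet transfusion or Grade 4 thrombocytopenia". Both introduce the list in the same way: "Dose-limiting toxicity is defined as one of the following toxicities (according to the NCI CTCAE Version 5.0". The neutrophil criterion prints its count (ANC below 500/µL). The platelet criterion prints none. To qualify, the event must be at least possibly related to UCB6114 and fall in Days 1 to 28 of Cycle 1.

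**Part B dosing table.** Table 6-9 lists, under CTCAE Grade 4, neutropenia below 0.5×10⁹/L "or thrombocytopenia (<25x10"×10⁹/L), where either delays the next cycle by more than a week.

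**Part C dosing table.** The grade column of Table 6-14 is headed "CTCAE (V5.0) Toxicity Grade". Its platelet rows, with the oxaliplatin and then the 5-fluorouracil instruction, are:
- Grade 3: "10 to <50 Reduce 1 dose level Maintain dose level"
- Grade 4: "<10 Reduce 2 dose levels Maintain dose level"

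The same table requires a hold when platelets are below 75 on Day 1 or Day 15, weekly counts during the hold, and a restart dose set by the lowest platelet result.

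**Grading in general.** Appendix 3 (section 11.3) requires AE intensity to be graded by CTCAE v5.0. Section 10.3.1 grades laboratory values by CTCAE where grades exist.

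**The concern.** A single grading scale cannot have two lower limits for Grade 3 platelets. The boundary matters more than most, because it separates an event that is a DLT only with bleeding or transfusion from one that is always a DLT.

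Table 6-14 is also hard for a Part C site to avoid. It is the only place in the Part C text where a platelet count is turned into a grade, it claims to be CTCAE v5.0, and its Grade 4 ANC row (below 0.5×10⁹/L) agrees with the ANC figure in the DLT section. A site has little reason to distrust the platelet rows.

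Incidence of DLTs and severity of TEAEs are primary endpoints of Part C (Table 3-2), and the DLT count is the input to the escalation table (Table 4-3). If the Part B figure is the correct one, the error runs in the unsafe direction: a DLT may not be put forward, and the next cohort may be escalated.

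**Working it through.** **1. The two boundaries side by side (platelets, ×10⁹/L)**

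| Count, no bleeding or transfusion | Grade by Table 6-9 | Grade by Table 6-14 | Meets platelet DLT criterion? |
|---|---|---|---|
| below 10 | 4 | 4 | yes under both |
| 10, 15, 24.9 | 4 | 3 | yes by Table 6-9, no by Table 6-14 |
| 25 to below 50 | not 4 | 3 | no under both |

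The range in conflict is exactly 10 to below 25. With bleeding or platelet transfusion, a count in that range is a DLT under either boundary, so only uncomplicated counts are affected. The Grade 3 and Grade 4 bands of Table 6-14 meet at 10, so the figure is not a digit lost in text extraction.

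**2. Does Table 6-14 come into play during the DLT window?** The window is Days 1 to 28 of Cycle 1. The table's hold rule applies on Day 15. A count of 18 then calls for a hold (18 is below 75) and for consulting the row that labels it Grade 3. So it does.

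**3. What one reclassified participant does to the decision.** I first reproduced the plan's Table 4-3. The inputs from section 4.1.5.2.2 are a target of 0.25 and an interval of 0.20 to 0.30. Two inputs are not stated and are assumed: a Beta(1,1) prior, and a dose declared unacceptably toxic when P(p > 0.25) exceeds 0.95. With x DLTs in n participants the posterior is Beta(1+x, 1+n−x). The decision is the interval with the largest unit probability mass (posterior probability divided by interval length). For n = 3:

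| x | Below 0.20 (÷0.20) | 0.20–0.30 (÷0.10) | Above 0.30 (÷0.70) | Decision |
|---|---|---|---|---|
| 0 | 0.5904/0.20 = 2.95 | 0.1695/0.10 = 1.70 | 0.2401/0.70 = 0.34 | escalate |
| 1 | 0.1808/0.20 = 0.90 | 0.1675/0.10 = 1.68 | 0.6517/0.70 = 0.93 | stay |
| 2 | 0.0272/0.20 = 0.14 | 0.0565/0.10 = 0.57 | 0.9163/0.70 = 1.31 | de-escalate |

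At x = 2, P(p > 0.25) = 0.949, just under 0.95, so the dose is not declared unacceptably toxic, as in the plan. Every cell of Table 4-3, for n = 3 to 9, is reproduced on these assumptions. With a 0.90 cut-off three cells differ, so 0.95 is the better match.

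Reading Table 4-3 with one DLT added:
- n = 3: 0→1 moves escalate to stay; 1→2 moves stay to de-escalate.
- n = 6: 0→1 moves escalate to stay; 2→3 moves stay to de-escalate; 1→2 changes nothing.
- n = 9: 1→2 moves escalate to stay; 3→4 moves stay to de-escalate.

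At every n from 3 to 9 there is at least one DLT count at which one more case changes the decision.

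**4. Oxaliplatin dose.** Section 6.6.3.4 gives the levels as 85, 65 and 50 mg/m². For a count of 18, the count band in Table 6-14 says one level down (65). If the participant has been graded 4 on the Part B figure, the grade column says two levels down (50), which uses up the two reductions allowed. The row to follow depends on whether the site enters the table by count or by grade.

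**The case against.** The strongest reply is that the DLT definition takes its grade from neither table. It cites CTCAE v5.0, and Appendix 3 requires the same scale for all AEs. One external standard therefore governs Parts B and C, and a site would have to bypass it and grade from a chemotherapy dosing table. Table 6-14 is also visibly not a full grading scale: its Grade 1 rows have no upper limit, so a normal count would be Grade 1. The SMC adjudicates individual DLTs (section 4.1.1), and investigators with the medical monitor can declare one.

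Most of this stands, and it rules out a stronger reading. A reader might infer that the DLT rule contradicts itself, or that DLT status formally depends on which table is used. The documents do not support that, since the rule points to CTCAE alone. Nor does every nadir of 10 to below 25 change status. It must also be uncomplicated, at least possibly related to UCB6114 and within Cycle 1; a nadir attributed only to mFOLFOX6 is not a DLT at either boundary.

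What does not fall away is that a table labelled with the governing scale conflicts with another table that also invokes CTCAE, and nothing in the protocol reconciles them. Adjudication helps only with events that are put forward, and an event entered as uncomplicated Grade 3 may not be.

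**Conclusion.** The inconsistency is real and stands in the current text. It is an error of labelling or of boundary in a dose-modification table, with a plausible route to misclassifying a primary-endpoint event. It is not a defect in the DLT rule.

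Its size is bounded: platelet counts of 10 to below 25×10⁹/L, uncomplicated, possibly UCB6114-related, in Cycle 1. Within those limits a single case can change an mTPI decision, and oxaliplatin may be reduced by one level or two. The frequency of such counts under mFOLFOX6 plus UCB6114 is not given, so the examples show what one case does and not how likely it is.

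The documents do not settle which count is the true CTCAE v5.0 boundary, and the conclusion does not need that.

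Two further inferences are not supported:
- Table 6-14 leaves 70 to below 75 without a grade. This changes no dose and no DLT: both neighbouring rows keep the dose, and the hold below 75 covers the gap.
- The Part A criteria (section 4.1.2.4) also name Grade 4 thrombocytopenia without a count, but Part A has no competing platelet table, so they need no change.

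**What to change.** 1. Check the Grade 4 platelet boundary against CTCAE v5.0. Then either correct the grade column of Table 6-14 to it, or remove the CTCAE label and define the rows by count alone. If v5.0 were to support the Table 6-14 figure, Table 6-9 is the one to correct.
2. Print that one Grade 4 platelet count in the DLT criteria of sections 4.1.4.2.1 and 4.1.5.2.1, as is already done for ANC.
3. Make clear which oxaliplatin reduction applies to counts of 10 to below 25. Which one is a clinical choice for the sponsor.
4. Check Part C platelet grades already entered, and any DLT decision that rested on a count in the affected range.

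Closing the 70 to below 75 gap at the same time is optional tidying. The cost is a wording and table correction in an amendment plus a short data check; no new data collection or change to the design is needed.

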##### **4.1.5.2.2 Determination of maximum-tolerated dose**

For every dose levels, participants will be treated in cohorts of 2 to 4 (target of 3), each dose level will have a minimum of 3 and a maximum of 9 participants.

The target rate of DLTs is 25% (equivalence interval 20% to 30%). The target rate will define the MTD of the combination regimen (UCB6114 given in combination with mFOLFOX6).

The mTPI method relies upon a statistical probability algorithm, calculated using data from all participants treated in prior and current cohorts at the same dose level, to determine whether future cohorts should be dose escalated, have no change in dose, or be dose de-escalated. The dose escalation will stop if any of the following criteria are met:

- The maximum sample size has been reached (27 participants total)
- At least 9 participants have been accumulated on a dose that is predicted to be the MTD
- All doses explored appear to be overly toxic and the MTD cannot be determined
- The escalation would exceed a dose level tested and considered safe by the SMC in monotherapy (Part A)

The mTPI design uses a Bayesian decision framework to inform dose-escalation and de-escalation decisions. These rules are conceptually similar to those used by the 3+3 design. The

dose-escalation decisions can be pre-calculated under the mTPI design and are presented in a 2-way table (Table 4-3).

**Table 4-3: Part C dose escalation/de-escalation schema for mTPI designa**

Number of DLTs	Number of participants treated at dose level						
	3	4	5	6	7	8	9
0	E	E	E	E	E	E	E
1	S	S	S	S	E	E	E
2	D	D	S	S	S	S	S
3	DR	DR	DR	D	S	S	S
4		DR	DR	DR	DR	DR	D
5			DR	DR	DR	DR	DR
6				DR	DR	DR	DR

D=de-escalate to next lower dose; DLT=dose-limiting toxicity; DR=the current dose is unacceptably toxic; E=escalate to next higher dose; mTPI= modified toxicity probability interval; S=stay at current dose

a Target toxicity=0.25

Table 4-3 has the following interpretation (using 3 and 6 treated participants as examples):

With 3 participants treated at current dose level:

- 0 DLTs = escalate
- 1 DLT = remain at the same dose
- 2 DLTs = de-escalate
- 3 DLTs = de-escalate and consider current dose as intolerable

With 6 participants treated at current dose level:

- 0 DLTs = escalate
- 1 to 2 DLTs = remain at the same dose
- 3 DLTs = de-escalate
- >3 DLTs = de-escalate and consider current dose as intolerable

#### **4.1.5.3 Defining the recommended Phase 2 dose in combination with mFOLFOX6**

The RP2D-F will be defined after all participants evaluable for DLT assessment in Part C have completed a minimum of 28 days of treatment (ie, 1 cycle). The RP2D-F will not exceed the RP2D-M or the MTD (if an MTD is established). The definition of the RP2D-F will take into account the safety profile, PK, PD biomarkers, and any antitumor effect data.

#### **4.1.6 Part D – Monotherapy 1 expansion**

Part D can be initiated as soon as the RP2D-M is determined in Part A, or commencement may be delayed until evaluation of other schedules or routes of administration in Part A1.

#### **4.1.7        Part E – Monotherapy 2 expansion**

Part E can be initiated as soon as the RP2D-M is determined in Part A, or commencement may be delayed until evaluation of other schedules or routes of administration in Part A1.

#### **4.1.8        Part F – Combination 1 expansion**

Part F can be initiated as soon as the RP2D-T is determined in Part B.

#### **4.1.9        Part G – Combination 2 expansion**

Part G can be initiated as soon as the RP2D-F is determined in Part C.

#### **4.1.10       Tumor type selection for modules post-Part A**

The tumor types to be explored in the modules following Part A will be selected based upon the following:

- Data collected through Part A
- Evolving preclinical and translational data
- Literature data on the role of gremlin-1 in specific tumors
- Feasibility of enrollment

The protocol may be amended to replace the tumor types based on emerging data.

### **4.2           Scientific rationale for study design**

This is a modular study comprising dose escalation and expansion modules.

The first dose escalation module of the study is an open-label, nonrandomized modified rolling-6 design (an algorithm-based extension of the 3+3 design which is a standard practice in Phase 1 oncology studies) in participants with advanced solid tumors, where UCB6114 will be administered as monotherapy.

Two additional dose escalation modules will explore combination regimens (Part B and Part C). These will use the mTPI design to guide dose escalation (Ji and Wang, 2013). This design has a low risk of exposing participants to doses above the MTD and yields high probabilities for identifying the correct MTD.

The planned monotherapy expansion modules and combination expansion modules will allow the simultaneous evaluation of multiple tumor types and standard of care regimens, replacing separate Phase 2 studies that would have followed after identification of the RP2D. Combining dose escalation and the expansion modules under one protocol will allow multiple hypotheses to be addressed (ie, different tumor types, doses) and potentially expedite development and approval of UCB6114.

#### **4.2.1        Rationale for Part A**

The rationale for Part A is provided in Section 2.1.

The tumor types for Part A were selected based on the reported prevalence of detectable expression and/or expression level of *GREM1* mRNA and include bladder urothelial carcinoma, breast invasive carcinoma, colorectal adenocarcinoma, esophageal carcinoma, head and neck

squamous cell carcinoma, lung adenocarcinoma, lung squamous cell carcinoma, pancreatic adenocarcinoma, prostate adenocarcinoma, and stomach adenocarcinoma.

#### **4.2.2 Rationale for Part A1**

*GREM1* mRNA expression has been reported in more than half of tissue samples from colorectal and pancreatic cancer (Sneddon et al, 2006). Upregulated gremlin-1 expression has been linked to a more advanced tumor stage and poor clinical prognosis in gastric cancer (Sun et al, 2020). In CRC, high levels of *GREM1* expression were associated with a shorter disease-free survival when compared with low levels of *GREM1* expression (Davis et al, 2015; Dutton et al, 2019).

Part A1 will be conducted in participants with colorectal-, gastric-, gastroesophageal junction or, pancreatic cancer and will evaluate alternative dosing schedules and duration of infusion to allow for future combination regimens with UCB6114 and a range of other treatments. Part A1 will use modifications to the 5th dose-level in Part A (2000mg Q2W) should this be determined to be ■ (i.e. DLT incidence <33%, see Section 4.1.2.4).

#### **4.2.3 Rationale for Part B and Part C**

UCB nonclinical data showed that, in the *ApcMin;Vil1-Grem-1* model of CRC in late stage, disease established mice, the combination of 5-fluorouracil and the murinized version of UCB6114, Ab7326 mIgG1, significantly prolonged mouse lifespan. This supports the evaluation of UCB6114 in selected gastrointestinal cancer types in combination with a fluoropyrimidine-based chemotherapy.

Trifluridine/tipiracil chemotherapy is used in different lines of treatment which depends on the tumor type, the patients' comorbidities, and personal preferences. As no overlapping toxicity is expected, in Part B the dose escalation of UCB6114 will start in combination with therapeutic doses of the TFD/TPI chemotherapy, with the expectation that participants will benefit from the standard of care chemotherapy.

The mFOLFOX6 chemotherapy regimen, consisting of leucovorin, 5-fluorouracil, and oxaliplatin, has been evaluated in CRC for more than 15 years and is commonly used in a variety of gastrointestinal cancers, including CRC and gastric- and gastroesophageal junction adenocarcinoma. The mFOLFOX6 chemotherapy regimen is used in different lines of treatment which depends on the tumor type, the patients' comorbidities, and personal preferences. As no overlapping toxicity is expected, in Part C the dose escalation of UCB6114 will start in combination with therapeutic doses of the mFOLFOX6 chemotherapy, with the expectation that participants will benefit from the standard of care chemotherapy.

#### **4.2.4 Dosing strategy**

The monotherapy dose escalation module (Part A) will systematically evaluate the safety, tolerability, and PK of UCB6114 at increasing dose levels.

The planned dose escalation steps are given in Table 6-5. In the event that exposure is substantially lower than anticipated, dose escalations will still not exceed a 5-fold increase. Doses will be administered every 2 weeks by iv infusion.

In Part A, the SMC will decide on the dose escalation steps (see Section 4.1.2.1). Based upon the emerging data, the SMC may decide to add up to 2 additional dose levels and/or schedules. Doses above 2000mg iv Q2W will be subject to a substantial amendment.

The combination dose escalation modules (Part B and Part C) will start with the Part A Cohort 3 dose of UCB6114. Depending on the eventual determination of the RP2D-M from Part A, this starting dose could represent 25% to 100% of the RP2D-M. Doses of UCB6114 in the combination dose escalation modules will not exceed the MTD if an MTD is determined. Combination agents will be given at the approved doses and schedules.

The RP2D-M will be used in the monotherapy expansion modules (Part D and Part E) and the RP2D in combination therapy will be used for the combination expansion modules (Part F and Part G).

### **4.3 Justification for dose**

#### **4.3.1 Starting dose in Part A**

The rationale to start at UCB6114 100mg administered iv Q2W in Part A is based on the following:

- The maintenance of a predicted suppression of gremlin-1 associated with antitumor activity (prolonged survival; predicted 95% suppression across the dosing interval) observed in nonclinical pharmacology models assuming a low level of gremlin-1 (████████) in human and a slow gremlin-1 turnover rate █████ based on a PK/PD model scaled to human developed using single ascending dose data from cynomolgus monkeys.
- The low risk of UCB6114's mechanism of action (antagonism of gremlin-1) and the class of molecule (fully human IgG4P), in combination with the lack of relevant adverse findings from the nonclinical 13-week GLP toxicity studies.

When Ab7326 mIgG1 (murinized version of UCB6114) was dosed iv at 30mg/kg twice weekly (BIW) in the *ApcMin/Vill-Grem1* model, or 30mg/kg once weekly (QW) in the *Vill-Grem1* model, a significantly increased survival over vehicle control was observed. Lower doses had reduced antitumor activity or had no effect, whereas higher doses did not appear to further increase survival. The human exposures at this dose level are anticipated to be lower than the exposures achieved at the efficacious doses identified in the nonclinical pharmacology models. These models are known to highly over-express gremlin-1 mRNA and may have much higher levels of gremlin-1 protein present than in patients with advanced solid tumors; therefore, the human exposures required for antitumor activity are anticipated to be lower. The median average concentration at steady state ( $C_{av,ss}$ ) anticipated following 100mg iv Q2W is 20.4 $\mu$ g/mL, which corresponds to a concentration 10-fold greater than the cellular IC50 for the ID-1 reporter assay (an in vitro assay measuring the functional inhibition of BMP signaling by gremlin-1). The FIH starting dose is anticipated to have a >100-fold safety margin based on the outcome of the 13-week GLP toxicity studies in cynomolgus monkeys and rats. Further details regarding dose modification are provided in Section 6.6.

